5.3 Adjustments for Covariates

No statistical tests will be performed.

5.4 Handling of Dropouts or Missing Data

Intercurrent events, as per the ICH guideline (ICH E9R1), are events which occur after the treatment initiation and make it impossible to measure a variable or influence how it should be interpreted. Examples of such events include treatment discontinuation due to death or AEs, rescue treatment, and loss to follow-up.

This section describes missing data imputation methods handling intercurrent events, which will be implemented in this study. For efficacy analyses relative to the primary estimand for primary and secondary endpoints, the method of handling missing data will be the “as observed” strategy described in Section 5.4.1.

For efficacy analyses relative to the supportive hypothetical estimands for primary and secondary endpoints, missing data including those because of intercurrent events will be imputed using the Last Observation Carried Forward (LOCF) strategy described in Section 5.4.2.

For efficacy analyses relative to the supportive hybrid estimands for primary and secondary endpoints, missing data including those because of intercurrent events will be imputed using Markov Chain Monte Carlo Multiple Imputation (MCMC-MI) as described in Section 5.4.3.

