Visit Interval Tolerance (Days)		—	±3	±3	±5	±5	±5	±5	±5	—	±7		
Visit Detail						T		T					
PROs (Electronic)													
Complete prior to any clinical administered assessments													
PO-SCORAD		X					X		X	X			
DLQI		X					X		X	X		Only for participants ≥16 years of age at baseline.	
cDLQI		X					X		X	X		Only for participants <16 years of age at baseline.	
WPAI-AD		X					X		X	X			
ADCT		X		X			X		X	X			
Participant-Reported Satisfaction Question							X		X	X			
Clinician-Administered Assessments (Electronic)													
IGA	X	X	X	X	X		X		X	X			
F-IGA		X	X	X	X		X		X	X			
EASI	X	X	X	X	X		X		X	X			
BSA	X	X	X	X	X		X		X	X			
PDS		X					X		X	X			
Clinician-Administered Assessments (Paper)													
Fitzpatrick Skin Type Assessment	X												

	Period I	Period II									Period III	Comments	
	Screening	Baseline	Treatment Period									Post-treatment Follow-Up	
Visit Number	1	2	3	4	5	6	7	8	9	ED	801		
Week Relative to Study Drug Start	≤30 (days)	0	2	4	8	12	16	20	24	—	12 weeks post last dose		
Visit Interval Tolerance (Days)		—	±3	±3	±5	±5	±5	±5	±5	—	±7		
Visit Detail						T		T					
Participant Education and Supplies													
Participant or caregiver instructions on diary completion	X											Education can also be performed on an as-needed basis.	
Remind participant of TCS usage restrictions and expectations	X											Required 2-week wash out of TCS prior to Visit 2. See Sections 6.8.1, 6.8.2, and 6.8.5 for TCS usage.	
Train participant and/or caregiver on study intervention administration			X	X								Participants and/or caregivers need to be adequately trained on injection technique prior to administering injections. Training can be done at Week 2 and/or Week 4 prior to self-administration.	
Dispense ancillary supplies				X	X		X						
Laboratory Tests and Sample Collections													
Hematology	X	X		X			X		X	X	X		
Clinical chemistry	X	X					X		X	X	X		
Serum pregnancy	X											Only for WOCBP. Pregnancy tests prior to first dose of study intervention for females ≥12 years of age if menarche reached or if there is reason to believe the participant is sexually active. Pregnancy test results from baseline must be known prior to first dose of study intervention. See Section 10.4, Appendix 4.	

	Period I	Period II									Period III	Comments	
	Screening	Baseline	Treatment Period									Post-treatment Follow-Up	
Visit Number	1	2	3	4	5	6	7	8	9	ED	801		

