5.2.2. Supportive Estimands for the Primary Endpoint

There are two supportive estimands for the primary endpoint. The first is a hybrid estimand representing the following clinical question of interest: What is the intervention effect in percentage of participants achieving at least 75% improvement from baseline in Eczema Area and Severity Index (EASI) after 16 weeks of lebrikizumab 250 mg Q2W intervention in participants with skin of color and moderate-to-severe AD if all participants adhered to treatment except those who discontinued due to lack of efficacy?

This estimand is described by the following attributes:

- A. Population: participants with skin-of-color and moderate-to-severe AD.
- B. Endpoint: whether participants achieve at least 75% improvement from baseline in EASI at Week 16.
- C. Intercurrent events (ICEs): One ICE, permanent treatment discontinuation, is considered by this estimand as follows:
 - a. Participants who discontinue treatment due to lack of efficacy prior to Week 16 will be considered as treatment failures, i.e. non-responders, after the ICE. Therefore, a composite strategy is used for this type of ICE.
 - b. For participants who discontinue treatment due to reasons other than lack of efficacy prior to Week 16, a hypothetical strategy will be used to estimate what the treatment effect would have been if subjects continued with treatment. Therefore, a hypothetical strategy is used for this type of ICE.
- D. Population-level summary: percentage of participants achieving EASI-75 response at Week 16.

The second supportive estimand for the primary endpoint is a hypothetical estimand representing the following clinical question of interest: What is the intervention effect in percentage of participants achieving at least 75% improvement from baseline in Eczema Area and Severity Index (EASI) after 16 weeks of lebrikizumab 250 mg Q2W intervention in participants with skin of color and moderate-to-severe AD if all participants adhered to treatment?

This estimand is described by the following attributes:

- A. Population: participants with skin of color and moderate-to-severe AD.
- B. Endpoint: whether participants achieve at least 75% improvement from baseline in EASI at Week 16.
- C. Intercurrent events (ICEs): One ICE, permanent treatment discontinuation, is considered by this estimand as follows:

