- a. For participants who discontinue treatment prior to Week 16, a hypothetical strategy will be used to estimate what the treatment effect would have been if all subjects continued with treatment. Therefore, a hypothetical strategy is used for this type of ICE.
- D. Population-level summary: percentage of participants achieving EASI-75 response at Week 16.

5.2.3. *Estimands for Secondary Endpoints at Week 16*

The primary estimand for the primary endpoint will be applied to all secondary endpoints at Week 16. The supportive estimands for the primary endpoint will also be applied to all secondary endpoints at Week 16.

5.2.4. *Estimands for Secondary Endpoints at Week 24*

The primary estimand for the primary endpoint will be applied to all secondary endpoints at Week 24. There are two supportive estimands for secondary endpoints at Week 24. The first is a hybrid estimand representing the following clinical question of interest: What is the intervention effect in successful responses or means after 24 weeks of lebrikizumab intervention in participants with skin of color and moderate-to-severe AD if all participants adhered to treatment except those who discontinued due to lack of efficacy?

This estimand is described by the following attributes:

- A. Population: Treatment Period II population as described in Section 5.1.1.
- B. Endpoint: apply to all secondary endpoints at Week 24.
- C. Intercurrent events (ICEs): One ICE, permanent treatment discontinuation, is considered by this estimand as follows:
 - a. Participants who discontinue treatment due to lack of efficacy after Week 16 will be considered as treatment failures, i.e. non-responders, after the ICE. Therefore, a composite strategy is used for this type of ICE.
 - b. For participants who discontinue treatment due to reasons other than lack of efficacy after Week 16, a hypothetical strategy will be used to estimate what the treatment effect would have been if subjects continued with treatment. Therefore, a hypothetical strategy is used for this type of ICE.
- D. Population-level summary: percentage of successful responses or means at Week 24.

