The second supportive estimand for secondary endpoints at Week 24 is a hypothetical estimand representing the following clinical question of interest: What is the intervention effect in successful responses or means after 24 weeks of lebrikizumab 250 mg Q2W intervention in participants with skin of color and moderate-to-severe AD if all participants adhered to treatment?

This estimand is described by the following attributes:

- A. Population: Treatment Period II population as described in Section 5.1.1.

- B. Endpoint: apply to all secondary endpoints at Week 24.
- C. Intercurrent events (ICEs): One ICE, permanent treatment discontinuation, is considered by this estimand as follows:
 - a. For participants who discontinue treatment after Week 16, a hypothetical strategy will be used to estimate what the treatment effect would have been if all subjects continued with treatment. Therefore, a hypothetical strategy is used for this type of ICE.
- D. Population-level summary: Population-level summary: percentage of successful responses or means at Week 24.

Because participants who initiate rescue medication are required to discontinue from the study and hence permanently discontinue study treatment, the supportive estimands for the primary and secondary endpoints only consider permanent treatment discontinuation as an ICE.

Analytical details on how missing data including those as a result of intercurrent events will be handled can be found in Section 5.4. The following table (Table KGBP.5.3) summarizes the analytical strategies that will be conducted on the intercurrent events for the five estimands.

Table KGBP.5.3 Description of Primary and Supportive Estimands

Estimand	Population	Analysis Strategy for the ICE of Permanent Treatment Discontinuation		Missing Data Imputation Method
		Due to lack of efficacy	Due to any other reasons, including initiation of rescue medication	
Primary Estimand for the Primary Endpoint and Secondary Endpoints	ITT Population who remained on treatment	Not applicable	Not applicable	Primary analysis: as observed
Supportive Estimand for the Primary Endpoint and Secondary Endpoints at Week 16 (Hybrid)	ITT Population	Composite: Set to baseline	Hypothetical: Set to missing	MCMC-MI
Supportive Estimand for the Primary Endpoint	ITT Population	Hypothetical: Set to missing	Hypothetical: Set to missing	LOCF

and Secondary Endpoints at Week 16 (Hypothetical)				

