5.4.1 As Observed Analysis

The “as observed” strategy is used in so-called “observed cases” or “completers” analysis ubiquitous in the literature but is not one of the recommended strategies in the ICH E9(R1). For this analysis, only data from completers at the visit are relevant. All efficacy data will be

summarized using an “as observed” analysis and summaries based on observed data at each postbaseline visit will be provided.

5.4.2 *Last Observation Carried Forward*

In this analysis, all missing values will be imputed using last observation carried forward (LOCF). Baseline values will be used for imputation if there is no postbaseline observation.

5.4.3. *Markov chain Monte Carlo - Multiple Imputation (MCMC-MI)*

The method of handling missing efficacy data relative to the supportive hybrid estimands for the primary and secondary endpoints at Week 16 will be based on Markov Chain Monte Carlo Multiple Imputation (MCMC-MI). For patients who discontinue treatment due to lack of efficacy prior to Week 16, set to the patient’s baseline value subsequent to this time through Week 16. MCMC-MI will be used to handle the remaining missing data.

The method of handling missing efficacy data relative to the supportive hybrid estimand for secondary endpoints at Week 24 will be based on MCMC-MI. For patients who discontinue treatment due to lack of efficacy after Week 16, set to the patient’s baseline value subsequent to this time through Week 24. MCMC-MI will be used to handle the remaining missing data.

Imputation will be conducted within each treatment group independently so that the pattern of missing observations in one treatment group cannot influence missing value imputation in another.

For each imputation process, 25 datasets with imputations will be calculated. The initial seed values are given in Table KGBP.5.3. The response rates and their associated SEs will be computed for each data set using SAS PROC FREQ with the riskdiff option specified for the appropriate column in the TABLES statement. The response rates and SEs from the resulting output will be combined across the 25 imputed datasets using SAS PROC MIANALYZE.

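### LOCF does not target the SAP's hypothetical full-adherence estimands; the bias is probably downward, but the documents do not fix its sign or size

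*SAP*

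**What the plan says.** SAP 5.2.2 defines the second supportive estimand for Week 16 EASI-75 in "participants with skin of color and moderate-to-severe AD if all participants adhered to treatment". The rule for the intercurrent event is explicit: "For participants who discontinue treatment prior to Week 16, a hypothetical strategy will be used". SAP 5.2.3 applies this to the secondary endpoints at Week 16, and SAP 5.2.4 sets up a parallel hypothetical estimand at Week 24 in the Treatment Period II population.

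Table KGBP.5.3 gives the data rule for both as "Hypothetical: Set to missing", whatever the reason for stopping, with LOCF as the imputation method. SAP 5.4 repeats that the values are "imputed using the Last Observation Carried Forward (LOCF) strategy described in Section 5.4.2", and SAP 5.4.2 adds: "Baseline values will be used for imputation if there is no postbaseline observation".

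The hybrid estimands share part of this. For discontinuation other than for lack of efficacy, Table KGBP.5.3 uses the same hypothetical strategy and the same set-to-missing rule. There, however, the missing data "will be imputed using Markov Chain Monte Carlo Multiple Imputation (MCMC-MI) as described in Section 5.4.3".

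The Protocol's Schedule of Activities has EASI at screening, at Weeks 0, 2, 4, 8, 16 and 24, and at the ED visit. The remote visits at Weeks 12 and 20 have none.

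**The concern.** The estimand and the estimator answer different questions. The estimand asks about a participant who stopped but is imagined to have stayed on lebrikizumab to the target week. LOCF assumes that the score remains where it was at the last assessment. The two agree only if nothing would have changed between that assessment and the target week. A participant with no postbaseline EASI is given a change of zero, and so is always an EASI-75 non-responder.

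The SAP is also inconsistent with itself. If nobody stopped for lack of efficacy, the hybrid and hypothetical estimands at Week 16 would be the same quantity, yet the SAP would report two estimates of it, one by MCMC-MI and one by LOCF. A gap between the two columns therefore cannot be read as the effect of treating lack-of-efficacy dropouts differently.

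At stake is whether the row labelled hypothetical means what it says, for EASI-75 and for every secondary endpoint at Weeks 16 and 24. A second issue is precision. SAP 5.11 reports Wilson intervals after LOCF as if the filled-in values had been observed.

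**Working it through.** **1. The plan's own figure.** SAP 4.2 tabulates a Wilson 90% interval of 40.96% to 59.04% at a 50% response with n = 80. At 50% the Wilson half-width reduces to z / (2 × √(n + z²)), with z = 1.645 and z² = 2.706. For n = 80 this is 1.645 / (2 × √82.706) = 9.04 points, which matches the table. All seven rows reproduce.

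**2. Bias formula.** Let d be the share who stop before Week 16, q their EASI-75 rate at the carried visit, and p_D the rate they would have reached at Week 16 had they adhered. Let p_C be the completers' rate.

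- Target: (1 − d) × p_C + d × p_D
- LOCF: (1 − d) × p_C + d × q
- Bias: d × (q − p_D)

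**3. Inputs.** SAP 4.2 anticipates a response of about 50%; taking p_D equal to that is an assumption. Neither document gives d, and neither gives an EASI time course from which to take q. Both are therefore shown as ranges. Bias in percentage points at p_D = 50%:

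| Dropout d | q = 0 | q = 30% | q = 40% | q = 50% | q = 60% |
|---|---|---|---|---|---|
| 5% | -2.5 | -1.0 | -0.5 | 0 | +0.5 |
| 10% | -5.0 | -2.0 | -1.0 | 0 | +1.0 |
| 20% | -10.0 | -4.0 | -2.0 | 0 | +2.0 |

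For example, 0.20 × (0.30 − 0.50) = -4.0 points, so LOCF would report 46.0% where the target is 50%. Only the cell with 20% dropout and q = 0 exceeds the planned half-width of 9.04 points.

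**4. Sensitivity to p_D.** Participants who stop may be poorer responders than average. If q and p_D are both halved, the bias halves. At 10% dropout with q = 20% and p_D = 25%, it is 0.10 × (0.20 − 0.25) = -0.5 points, against -1.0 in the table.

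**5. An endpoint where the sign is fixed.** DLQI is scheduled only at baseline, Weeks 16 and 24, and the ED visit. For someone who stops before Week 16 without a usable ED value, LOCF carries baseline. On the 4-point responder endpoint q is then 0 and the bias is −d × p_D. With p_D assumed at 50% to 80% and 10% dropout, that is -5 to -8 points.

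**6. Precision.** The formula in step 1, at 50% response:

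- n = 80 counted as observed under LOCF: 9.04 points
- 72 observed (10% missing): 1.645 / (2 × √74.706) = 9.52 points
- 64 observed (20% missing): 1.645 / (2 × √66.706) = 10.07 points

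For the current Protocol's 95 participants, the half-width is 8.32 nominal and 9.27 with 76 observed. The observed-only widths are a guide rather than what MCMC-MI would return, since earlier visits recover some information.

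**The case against.** The strongest objection is that this matters little. The primary analysis is as observed, no hypothesis is tested, and Protocol 7.2 foresees few discontinuations. At 5% dropout with q of 30% to 40%, the bias is -0.5 to -1.0 points, well inside the interval. An MCMC-MI result is already planned for the same endpoints under the hybrid estimands. All of this stands and limits the weight of the point. It does not make LOCF an estimator of the stated question.

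Three stronger readings are tempting, and the documents do not support them.

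- *LOCF must understate the response.* The sign is that of q − p_D, and no time course is given. If early response had plateaued the bias is zero, and if it would have been lost the bias is upward. Protocol 4.3 reports that inadequate responders in Phase 3 gained from continued dosing. That makes a downward bias more likely, but it is indirect support.
- *Every dropout is frozen at Week 8 or earlier.* This holds only for scheduled EASI visits and the Week 16 endpoint. Protocol 7.1 and 7.2 route participants who stop through an ED visit, where EASI is scored. The SAP does not say whether that score may be carried forward or is removed by the set-to-missing rule. At Week 24 the last scheduled EASI is Week 16. The daily diary scores and the weekly POEM have no gap between Weeks 8 and 16.
- *Dropouts would have responded like everyone else.* Protocol 6.8.4, 6.8.5 and 7.1 require discontinuation after rescue, so some dropout reflects poor response, and p_D for those participants may be well below 50%.

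**Conclusion.** The mismatch holds. LOCF does not estimate the hypothetical estimands at Week 16 or Week 24, and it is inconsistent with the method the SAP uses for the same strategy elsewhere. The bias is probably downward. The EASI-75 sizes in the table are conditional on assumed values for dropout, for response at the carried visit and for response under adherence, none of which the documents supply for participants who stop. No single figure can be defended. The interval after LOCF is somewhat too narrow, by about half a point at 10% missing (9.52 − 9.04 = 0.48) and about one point at 20% (10.07 − 9.04 = 1.03), if observed-only precision is the yardstick.

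A reader might infer that the trial's main result is compromised. It is not, because LOCF is confined to supportive, descriptive summaries. The point is worth correcting because a labelled estimate and its interval should match their stated question.

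**What to change.** For the hypothetical estimands at Weeks 16 and 24, keep the set-to-missing rule and impute with the MCMC-MI of SAP 5.4.3, omitting the step that sets lack-of-efficacy dropouts to baseline. State that this relies on data being missing at random given the observed visits. Retain LOCF, if wanted, only as a sensitivity analysis labelled as such. Amend Table KGBP.5.3, SAP 5.4 and SAP 5.4.2 to agree.

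State whether an ED-visit value is used or set to missing and, if used, to which analysis visit it is assigned. The same rule should serve the hybrid estimands.

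The cost is SAP wording, one further run of imputation code already needed for the hybrid estimands, and extra seeds if separate streams are wanted. The seed table in SAP 5.4.3 already covers the EASI, IGA, Pruritus NRS, Sleep-Loss, Skin Pain NRS, DLQI, cDLQI and POEM analyses. No data collection changes, and these estimands are defined only in the SAP.

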5.4.1 As Observed Analysis

The “as observed” strategy is used in so-called “observed cases” or “completers” analysis ubiquitous in the literature but is not one of the recommended strategies in the ICH E9(R1). For this analysis, only data from completers at the visit are relevant. All efficacy data will be

summarized using an “as observed” analysis and summaries based on observed data at each postbaseline visit will be provided.

5.4.2 *Last Observation Carried Forward*

In this analysis, all missing values will be imputed using last observation carried forward (LOCF). Baseline values will be used for imputation if there is no postbaseline observation.

5.4.3. *Markov chain Monte Carlo - Multiple Imputation (MCMC-MI)*

The method of handling missing efficacy data relative to the supportive hybrid estimands for the primary and secondary endpoints at Week 16 will be based on Markov Chain Monte Carlo Multiple Imputation (MCMC-MI). For patients who discontinue treatment due to lack of efficacy prior to Week 16, set to the patient’s baseline value subsequent to this time through Week 16. MCMC-MI will be used to handle the remaining missing data.

The method of handling missing efficacy data relative to the supportive hybrid estimand for secondary endpoints at Week 24 will be based on MCMC-MI. For patients who discontinue treatment due to lack of efficacy after Week 16, set to the patient’s baseline value subsequent to this time through Week 24. MCMC-MI will be used to handle the remaining missing data.

Imputation will be conducted within each treatment group independently so that the pattern of missing observations in one treatment group cannot influence missing value imputation in another.

For each imputation process, 25 datasets with imputations will be calculated. The initial seed values are given in Table KGBP.5.3. The response rates and their associated SEs will be computed for each data set using SAS PROC FREQ with the riskdiff option specified for the appropriate column in the TABLES statement. The response rates and SEs from the resulting output will be combined across the 25 imputed datasets using SAS PROC MIANALYZE.

For binary responses related to EASI and IGA, the binary response variables will be calculated based on the multiply imputed datasets that have been created. Because the MCMC algorithm is based on the multivariate normal model, imputed values for IGA will not generally be one of the discrete values used in IGA scoring (0, 1, 2, 3, or 4). Therefore, to derive the binary IGA response variable, standard rounding rules will be applied to the imputed values. For example, if a patient has an IGA score imputed as 1.4 (and assuming a baseline IGA score of 3), the imputed value would be rounded down to 1, and the minimum change from baseline of 2 would have been met. This patient would be considered a responder.

For derivation of an EASI-75 and EASI-90 response, no rounding will be performed. The imputed EASI value will be compared directly to the observed baseline EASI value to determine whether a reduction of at least 75% or 90% was achieved at each visit.

For derivation of the following Pruritus NRS, Skin Pain NRS, Sleep-Loss Scale, and DLQI responses, no rounding will be performed. The imputed Pruritus NRS, Skin Pain NRS, and Sleep-Loss Scale values will be compared directly to the observed mean baseline values to

determine whether a response was achieved. The imputed DLQI values will be compared directly to the observed baseline values to determine whether a response was achieved.

- Proportion of patients with a Pruritus NRS of ≥ 3 points at baseline achieving at least a 3-point reduction by visit.
- Proportion of patients with a Pruritus NRS of ≥ 4 points at baseline achieving at least a 4-point reduction by visit.
- Proportion of patients with a Skin Pain NRS of ≥ 4 points at baseline achieving at least a 4-point reduction by visit.
- Proportion of patients with a Sleep-Loss Scale of ≥ 2 points at baseline achieving at least a 2-point reduction by visit.
- Proportion of patients with DLQI of ≥ 4 points at baseline achieving at least a 4-point reduction by visit.

Note that the estimate and 90% confidence interval bounds output by this SAS PROC MIANALYZE are percents (i.e, they are in terms of the response rate). To obtain the number of responders, the estimated percent is multiplied by the number of individuals in the analysis population and rounded to the nearest integer.

Imputation of continuous data will parallel that of binary variables. IGA, EASI, Sleep-Loss, Skin Pain NRS, Pruritus NRS, DLQI, CDLQI, and POEM will be summarized using an MCMC-MI analysis.

Table KGBP.5.5. Seed Values for MCMC-Multiple Imputation

Analysis	Seed Values for Weeks 0-16 of the Treatment Period; LEB 250mg Q2W	Seed Values for Weeks 16-24 of the Treatment Period; LEB 250mg Q2W or Q4W
Proportion of patients achieving IGA of 0 or 1 with a ≥ 2 point improvement from baseline by visit.	661769200	893745627
Percent change from baseline in EASI score by visit. EASI-75 and EASI-90 will leverage imputation from EASI and therefore use the same seed numbers.	153233047	345987238
Change from baseline in Pruritis NRS Score by visit. Proportion of patients with a Pruritis NRS Score of ≥ 3 or ≥ 4 points at baseline achieving at least a 3-point or 4-point reduction will leverage imputation from Pruritis NRS Score and therefore use the same seed numbers.	502899349	302781834
Change from baseline in Sleep-Loss Scale by visit. Proportion of patients with a Sleep-Loss Scale of ≥ 2 points at baseline who achieve at least a 2-point reduction at each visit will leverage imputation from Sleep-Loss Scale and therefore use the same seed numbers.	691405299	999692612
Change from baseline in Skin Pain NRS from baseline by visit. Proportion of patients with a Pruritis NRS Score of ≥ 4 points at baseline achieving at least a 4-point reduction will leverage imputation from Pruritis NRS Score and therefore use the same seed numbers.	81969226	20532741
Change from baseline in DLQI by visit. Proportion of patients with DLQI ≥ 4 points at baseline achieving at least a 4-point reduction will leverage imputation from DLQI and therefore use the same seed numbers.	66350098	60458640
Change from baseline in cDLQI by visit.	93794488	34792747
Change from baseline in POEM by visit.	90372455	71154458

Abbreviations: CDLQI = Children's Dermatology Life Quality Index; DLQI = Dermatology Life Quality Index ; EASI = Eczema Area and Severity Index; EASI-75 = Eczema Area and Severity Index improvement of $\geq 75\%$; EASI-90 = Eczema Area and Severity Index improvement of $\geq 90\%$; IGA = Investigator's Global Assessment for Atopic Dermatitis; LEB = lebrikizumab; MCMC = Markov chain Monte Carlo; NRS = Numeric Rating Scale; POEM = Patient-Oriented Eczema Measure; Q2W = every 2 weeks; Q4W = every 4 weeks.

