5.1.1 Analysis Populations

Analysis populations are defined in Table KGBP.5.1 along with the analyses they will be used to conduct. The number of patients included in each population will be summarized.

Table KGBP.5.1.1 Analysis Populations

Population	Description
All Entered Patients	All patients who signed informed consent. Patient flow will be summarized.
Intent-to-Treat (ITT) Population	All enrolled patients according to their planned intervention. Unless otherwise specified, efficacy and health outcomes analyses for Weeks 0 to 16 of the Treatment Period will be conducted on this population.
Safety Population	All enrolled patients who received at least 1 confirmed dose of lebrikizumab 250 mg. Safety analyses will be conducted on this population.
Treatment Period II Population	All enrolled patients who received at least 1 confirmed dose of lebrikizumab 250 mg during Weeks 16 to 24 of the Treatment Period. Unless otherwise specified, efficacy and health outcomes analyses for Weeks 16 to 24 of the Treatment Period will be conducted on this population.

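### The SAP's rule for multiply imputed responder counts uses the full analysis population, so displayed counts are too high for the five baseline-restricted endpoints whenever some patients do not qualify

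*SAP*

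**What the plan says.** SAP 5.4.3 pools response rates and standard errors over 25 imputed datasets. It notes that the estimate and 90% bounds "output by this SAS PROC MIANALYZE are percents" and then gives a single rule for the number of responders: "the estimated percent is multiplied by the number of individuals in the analysis population and rounded to the nearest integer".

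Just before that rule it lists five responder endpoints whose percentage is defined among patients at or above a baseline score. Sleep-Loss is limited to patients with 2 or more "points at baseline achieving at least a 2-point reduction by visit". Skin Pain, the stricter Pruritus endpoint and DLQI are limited to those with 4 or more "points at baseline achieving at least a 4-point reduction by visit". The other Pruritus endpoint uses 3 points. Protocol Section 3 and SAP Table KGBP.3.1 also limit the DLQI responder endpoint to participants aged 16 or over at baseline.

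Analysis population is a defined term. SAP 5.1.1 states: "Analysis populations are defined in Table KGBP.5.1 along with the analyses they will be used to conduct". The table lists All Entered, ITT, Safety and Treatment Period II. ITT, used to Week 16, is "All enrolled patients according to their planned intervention". For Treatment Period II, "efficacy and health outcomes analyses for Weeks 16 to 24 of the Treatment Period will be conducted on this population". No population is defined by a baseline score.

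In the seed table in the same section (Table KGBP.5.5), the Skin Pain row reads "Change from baseline in Skin Pain NRS from baseline by visit. Proportion of patients with a Pruritis NRS Score of" and then refers to the Pruritus imputation.

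**The concern.** The pooled percentage for a restricted endpoint describes m qualifying patients. A programmer who takes the defined term at face value multiplies that percentage by N, the size of ITT or Treatment Period II. The product is not the number of responders unless m equals N.

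The documents give three reasons to expect m below N:

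- Protocol 5.1 sets entry minimums for EASI, IGA and BSA, but none for itch, skin pain, sleep loss or DLQI.
- Under SAP 5.1.2, a patient with three or fewer diary responses in the baseline week has no baseline mean for the three diary scales.
- Enrollment starts at age 12, while the Schedule of Activities gives the DLQI only to those aged 16 or over.

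SAP 5.11 and 5.12 require a number alongside each percentage for the MCMC-MI summaries, so the count will be printed. A table whose count, percentage and true denominator disagree invites wrong recalculation and can show more responders than eligible patients. These are secondary endpoints at Weeks 16 and 24.

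**Working it through.** **The plan's own figure.** The plan prints no responder count, so there is none to reproduce on this point. The nearest stated figure is the Wilson 90% table for n = 80 (Protocol 9.5, SAP 4.2). At p = 0.50 with z = 1.645, the half-width is z × √(p(1−p)/n + z²/(4n²)) / (1 + z²/n) = 1.645 × √(0.003125 + 0.000106) / 1.0338 = 0.0904, giving 40.96% to 59.04% as printed. The other six rows also agree to two decimals. This table does not depend on the count rule.

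**Inputs.**
- N = 80 (SAP 4.1.1) or 95 (current Protocol 9.5). The Week 24 population, Treatment Period II, may be smaller.
- Illustrative response rate r = 50%. This is the plan's EASI-75 expectation, not a rate for itch, pain, sleep or DLQI. The ratio below does not depend on r.
- m/N: not in the documents. Assumed range 100% to 60%.

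**Formulas.** Count under the rule = round(r × N). Count for the endpoint = round(r × m). Ratio before rounding = N/m.

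**Results for N = 80, r = 50%.**

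| m/N | m | Endpoint count | Count under the rule | N/m |
|---|---|---|---|---|
| 100% | 80 | 40 | 40 | 1.00 |
| 90% | 72 | 36 | 40 | 1.11 |
| 80% | 64 | 32 | 40 | 1.25 |
| 70% | 56 | 28 | 40 | 1.43 |
| 60% | 48 | 24 | 40 | 1.67 |

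At N = 95 and m = 76 (80%), the endpoint count is 38 and the rule gives 47.5, rounded to 48. At m = 57 (60%), the values before rounding are 28.5 and 47.5, ratio 95/57 = 1.67. The ratio should be taken before rounding: with 28.5 taken down and 47.5 up, 48/28 = 1.71, which is a rounding artefact.

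**Impossible counts.** r × N exceeds m whenever r exceeds m/N. With N = 80, m = 40 and r = 60%, the rule gives 48 responders among 40 eligible patients.

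**How few patients matter.** For N = 80 or 95 and rates of 40%, 50%, 60% or 70%, one or two non-qualifying patients are enough to change the rounded count.

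**Seed table.** Read literally, the Pruritus endpoint at 4 points has two Weeks 0-16 seeds: 502899349 from the Pruritus row and 81969226 from the Skin Pain row. The Skin Pain responder endpoint is not named in its own row.

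**The case against.** The best defence is that the wording is loose rather than wrong. Each of the five endpoints names its baseline restriction, and the population table allows for exceptions where something else is specified. On that view the phrase means the patients in that particular analysis, and the counts come out right. This reading is possible, but the text does not state it. The exception clause governs which population is analysed, and no sentence in 5.4.3 narrows the multiplier. Elsewhere the SAP writes a restricted denominator out: for sex-specific adverse events (SAP 5.13.2), only patients of the relevant sex count as at risk.

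The objection on scope stands in full. The rule serves only the supportive hybrid estimands (SAP 5.4, Table KGBP.5.3), and the count is derived after the percentage and interval have been produced.

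Three stronger readings are tempting, and the documents do not support them:

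- *That rates or intervals are biased.* SAP 5.4.3 takes estimate and bounds from PROC MIANALYZE. SAP 5.11 and 5.12 do mention Wilson intervals for the MCMC-MI summaries, but nothing says to build them from the back-calculated count and N.
- *That every restricted endpoint will certainly be inflated.* If all patients qualify, m = N and the count is correct.
- *That Skin Pain responders have no imputation source.* SAP 5.4.3 says imputed Skin Pain values are compared with the observed baseline mean and lists the scale among those imputed. Its row has its own heading and seeds. The wrong instrument name is a copying slip.

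**Conclusion.** The rule is wrong as written, with limited reach. Taken with the SAP's own definition of analysis population, it overstates the displayed number of responders by N/m for each of the five restricted endpoints in which at least some patients do not qualify or lack a baseline value. The factor is about 1.11 to 1.67 if 90% to 60% qualify. That range is an assumption, because the documents give no basis for m/N. It is likely, though not certain, that m falls below N for at least some of these endpoints.

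The error stays in one displayed number in the supportive MCMC-MI tables. Pooled percentages, standard errors, MIANALYZE intervals, the as-observed primary analysis, the LOCF analysis, and the EASI and IGA counts do not change. No hypothesis is tested, so no decision depends on it. It still merits correction, because the printed count would contradict the percentage beside it.

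**What to change.** In SAP 5.4.3, limit the multiplier to those members of the analysis population who meet that endpoint's baseline-score restriction (and, for DLQI, the age restriction) and have the baseline value needed to establish it. Print that denominator in each MCMC-MI table so that count, percentage and denominator can be checked against each other.

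As a separate clerical correction, change the Pruritus NRS references in the Skin Pain row of Table KGBP.5.5 to Skin Pain NRS. SAP 5.4.3 also points to Table KGBP.5.3 for the seeds, which is the estimand table. That cross-reference can be corrected at the same time.

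The cost is a few words in the SAP and a check of the table shells. Design, data collection and imputation model are unchanged.
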